NON-INTERVENTIONAL (NI) STUDY PROTOCOL

Study Information

Title	The impact of RF, and anti-CCP on RA patients in response to Etanercept
Protocol number	B1801417
Protocol version identifier	3.0
Date	27 July 2021
Active substance	etanercept
Medicinal product	etanercept
Research question and objectives	The RF and anti-CCP are found to be positive in 70% and 65% of RA patients respectively. Researchers have found that RF and anti-CCP have an impact on RA response. The objective is to evaluate the impact of RF and ACCP on RA patients in response to Enbrel from the local data.
Author	PPD [REDACTED] – MD, M.Sc. PPD [REDACTED] Pfizer Inc. - Iraq
This document contains confidential information belonging to Pfizer. Except as otherwise agreed to in writing, by accepting or reviewing this document, you agree to hold this information in confidence and not copy or disclose it to others (except where required by applicable law) or use it for unauthorized purposes. In the event of any actual or suspected breach of this obligation, Pfizer must be promptly notified.	

PFIZER CONFIDENTIAL

[figure not shown]
[REDACTED]

2. LIST OF ABBREVIATIONS

[figure not shown]
Abbreviation	Definition
ACR	American College of Rheumatology
AE	Adverse Event
anti-CCP	Anti-Cyclic Citrullinated Peptide
CDAI	Clinical Disease Activity Index
DAS28	Disease Activity Score 28
DMARD	Disease -Modifying Antirheumatic Drug
EULAR	The European League Against Rheumatism
GEP	Good Epidemiological Practice
GGP	Guidelines for Good Pharmacoepidemiology Practices
IEA	International Epidemiological Association
IEC	Independent Ethics Committee
IRB	Institutional Review Board
ISPE	International Society for Pharmacoepidemiology
ISPOR	International Society for Pharmacoeconomics and Outcomes Research
MTX	Methotrexate
NA	Not Applicable
NSAIDs	Nonsteroidal Anti-Inflammatory Drugs
RA	Rheumatoid Arthritis
RF	Rheumatoid Factor

4. AMENDMENTS AND UPDATES

Amendment number	Date	Protocol section(s) changed	Summary of amendment(s)	Reason
1	22 June 2021	Section 5. Milestones	Updated to align with Study Report	Administrative
2	27 July 2021	Throughout the document	Spelling errors	Administrative

PFIZER CONFIDENTIAL

5. MILESTONES

Milestone	Planned date	Actual Date
Start of data collection	01 July 2020	01 July 2020
End of data collection	01 August 2020	01 August 2020
Final study report	30 June 2021	29 June 2021

6. RATIONALE AND BACKGROUND

In the past 1–2 decades, treatment paradigms in rheumatoid arthritis (RA) have shifted dramatically from initial treatment with nonsteroidal anti-inflammatory drugs (NSAIDs), followed by cautiously progressive addition of disease-modifying antirheumatic drugs (DMARDs), to the current treatment approach of aggressive initiation of DMARD therapy soon after the diagnosis of RA has been made. This change in RA management results from increasing data supporting improved prognosis and outcomes with the initiation of DMARD therapy early in the course of symptomatic disease.^{1,3}

Rheumatoid factor (RF) has long been a component of the diagnostic criteria for rheumatoid arthritis and although it positive in 70% of RA patients. RF is well studied and its associations with a more severe disease course have been extensively described in Western countries. In more recent years, anti-CCP was positive in 65%-80% of RA patients. The anti-CCP status provides important prognostic information in RA. Also, Rönnelid et al showed that anti-CCP seropositive patients had more active disease during follow-up than seronegative patients.²

Given the optionality of biological treatment for RA patients, identifying a predictor for response will required more attention from rheumatologists for such patients.⁴

7. RESEARCH QUESTION AND OBJECTIVES

The objective of this study is to evaluate the impact of RF and anti-CCP positivity on RA patients.

8. RESEARCH METHODS

8.1. Study Design

- **Retrospective analysis** of patients with RA that received etanercept from Baghdad Teaching Hospital (Rheumatology center) from May 2012 until August 2019 (inclusion and exclusion criteria will apply for selecting patients).
- **Primary objective:** Determine the clinical impact of RF and anti-CCP for management (etanercept) in patients with RA compared to negative RF and anti-CCP in RA patients.

8.2. Setting

Patients and Methods

Data will be collected from the Baghdad Teaching Hospital registry. The rheumatology patient registry is a prospective longitudinal multicenter cohort initiated in 2012. It captures all patients treated with biologic therapies managed in the rheumatology department. The decision to initiate and maintain the treatment is guided by the American College of Rheumatology (ACR) recommendations.

Study population

Patients will be included in the study if they meet the American College of Rheumatology/The European League Against Rheumatism (EULAR) 2010 criteria for Rheumatoid Arthritis,⁵ with at least 1 year of follow-up after starting their first biologic therapy. This includes patients who were in monotherapy or in combo-therapy with concomitant conventional DMARDs.

Hypothesis

Our hypothesis is that there is no difference in response between seropositive and seronegative RA patients to Enbrel.

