8.2.1. Inclusion Criteria

Patients must meet all the following inclusion criteria to be eligible for inclusion in the study:

1. Diagnosed RA patients.
2. ≥ 18 years of age.
3. Did not receive previous another biological treatment.

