8.6. Data Analysis

Categorical covariates will be described by frequency distribution while continuous covariates will be expressed in terms of their mean and standard deviation or median and interquartile range as appropriate. Patients will be divided for seropositive RA and seronegative RA (according to anti-CCP status). The unadjusted comparisons between groups of the covariates and the outcomes will be evaluated using chi² tests for categorical data, while for continuous data, the Student's t-test will be used for normally distributed variables and the Kruskall-Wallis test for non-parametric data.

The effect of biologic treatment response in patients with sero-positive RA will be determined with a multivariate analysis by using a stepwise linear regression model. The response variable is defined as DAS28 and CDAI at last visit. The baseline variables considered demographic data, disease duration (years), methotrexate (yes/no), current steroid therapy (yes/no), baseline DAS28 and CDAI, RF positive (yes/no), anti-CCP (yes/no), and present smoking (yes/no).

The effect of response will be determined by using change from baseline in DAS28 and CDAI at the last visit. A p-value of <0.05 is considered statistically significant, without multiplicity adjustment, for this post-hoc analysis.

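### Sections 8.2 and 8.2.1 define the study population differently, serology may be part of the entry test, and section 8.6 does not guarantee adjustment for baseline DAS28/CDAI

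*Combined protocol and SAP*

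**What the plan says.** **Population.** Section 8.2 (Study population) states: "Patients will be included in the study if they meet the American College of Rheumatology/The European League Against Rheumatism (EULAR) 2010 criteria for Rheumatoid Arthritis". It adds a minimum follow-up after the first biologic. Section 8.2.1 opens with "Patients must meet all the following inclusion criteria to be eligible for inclusion in the study", and its only disease criterion is "Diagnosed RA patients". It does not refer back to 8.2 or name a criteria set. Section 8.2.2 does not mention the criteria either.

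**Exposure.** Section 7 sets out to "evaluate the impact of RF and anti-CCP positivity on RA patients". Section 8.6 forms the groups by anti-CCP alone: "Patients will be divided for seropositive RA and seronegative RA (according to anti-CCP status". RF is a candidate covariate.

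**Serology in diagnosis.** Section 6 says: "Rheumatoid factor (RF) has long been a component of the diagnostic criteria for rheumatoid arthritis".

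**Analysis.** Section 8.6 plans unadjusted comparisons of the outcomes between groups (chi-square, t-test or Kruskal-Wallis). It also plans a stepwise linear regression of last-visit DAS28 and CDAI, with baseline DAS28 and CDAI among the candidates. It then adds: "The effect of response will be determined by using change from baseline in DAS28 and CDAI at the last visit". No covariate is named for that last analysis.

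**The concern.** Two analysts could each follow the protocol and build different cohorts. Section 8.3 does not list criteria status among the variables to be obtained, so a reader of the results could not tell which cohort was used.

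In many studies this would be only a drafting matter. Here the ambiguity touches the exposure. If serology earns credit towards entry, a seropositive patient can enter with less of everything else, and a seronegative patient has to make up the difference. Should those other features track disease activity, the seronegative group would start with higher DAS28/CDAI. A group that starts higher tends to fall further and still to end somewhat higher. Both an unadjusted change score and an unadjusted last-visit score could then show a serostatus difference that comes from entry and not from response to etanercept. Section 8.8 lists only missing data as a limitation.

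**Working it through.** The plan gives no sample size, power or effect size, so there is no figure of its own to reproduce. The check is textual first. The arithmetic that follows is an illustration.

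**1. Are the two rules equivalent?** 8.2 needs a named criteria set to be met; 8.2.1 needs a diagnosis. A diagnosed patient who does not meet the 2010 set is in under 8.2.1 and out under 8.2. Section 8.1 says that the inclusion and exclusion criteria select the patients, which points to the 8.2.1 and 8.2.2 lists. Nothing says which text governs.

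**2. Is serology part of entry?** Section 6 supports this for RF and for RA diagnosis in general. The documents do not reproduce the 2010 items, weights or threshold, and do not say that anti-CCP is an item. Because section 6 speaks of diagnosis, the 8.2.1 rule may also involve serology.

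**3. Does 8.6 protect against a baseline gap?** The unadjusted tests do not. The change analysis names no adjustment. The regression offers baseline as a candidate, and stepwise selection may drop it.

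**4. Illustration A: a rule that removes some seronegative patients.** All inputs here are assumptions, except that the 70:30 split borrows the 70% RF-positive figure in section 6. The true serostatus effect is zero. A non-serological entry score Z has correlation r with baseline activity. The rule removes the lowest fraction f of seronegative patients by Z. The last-visit score keeps b = 0.3 of baseline. Baseline and last-visit scores have unit SD before selection.

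- Baseline gap = r × φ(q_f)/(1 − f), where q_f is the f-quantile of the standard normal.
- Gap in change = (b − 1) × baseline gap. Gap at last visit = b × baseline gap.
- For r = 0.5 and f = 0.25: 0.5 × 0.318/0.75 = 0.21 SD. Gap in change = −0.7 × 0.21 = −0.15 SD.

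| f (r = 0.5) | Baseline gap, SD | Gap in change, SD | Rejection on change, n = 200 | Rejection on change, n = 500 | Rejection on last visit, n = 500 |
|---|---|---|---|---|---|
| 0.10 | 0.10 | −0.07 | 6% | 9% | 6% |
| 0.25 | 0.21 | −0.15 | 12% | 25% | 10% |
| 0.50 | 0.40 | −0.28 | 34% | 68% | 24% |

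The rejection rates are for the equal-variance t-test at two-sided 0.05 (4,000 simulated studies each; reruns agree within about one percentage point). With r from 0.3 to 0.7 the baseline gap runs from 0.06 to 0.56 SD.

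**5. Illustration B: a lower threshold for seropositive patients.** The seropositive threshold is lower by w = 0.5 to 1.5 SD (assumed), with correlation ρ. The gap is ρ × [φ(0)/0.5 − φ(w)/Φ(w)]. The bracket is 0.29 at w = 0.5 and 0.66 at w = 1.5, so the gap is 0 at ρ = 0, 0.14 to 0.33 SD at ρ = 0.5, and 0.23 to 0.53 SD at ρ = 0.8.

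**6. Selection for starting a biologic.** If all patients must also have baseline activity more than 0.5 SD above the mean (assumed), the gap in illustration B falls to 0.06 SD or less. In illustration A with r = 0.5, a cut at the median leaves about 0.01, 0.04 and 0.10 SD. A cut at the 25th percentile leaves 0.03, 0.08 and 0.18 SD. The documents state no activity threshold, so the size of this shrinkage is unknown.

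**7. With baseline in the model.** In illustration A the rejection rate for serostatus is 4% to 6% throughout. In illustration B the bias is within 0.01 SD. When baseline is a covariate, regressing change or the last-visit score gives the same serostatus coefficient, because the two outcomes differ only by the baseline score itself.

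**The case against.** The case on the other side has five parts.

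- **8.2.1 may be shorthand for 8.2.** Both sit under one heading. This is possible, but 8.2.1 presents itself as the list that governs eligibility and does not refer back, so the mismatch stands.
- **The mechanism is not in the documents.** They do not say that anti-CCP, the grouping variable, is an item of the 2010 set. The only activity comparison they give, in section 6, has anti-CCP-positive patients more active during follow-up. That concerns disease course, so it does not rule out a selection effect at entry, but it gives no support for one. This objection stands.
- **A baseline-adjusted regression is already planned.** This largely stands for the last-visit model. Under illustration A baseline is significant in 98% to 99% of runs at n = 200 and in all runs at n = 500, so stepwise selection would seldom drop it. It remains unguaranteed, and neither the unadjusted tests nor the change analysis is protected.
- **Everyone started a biologic**, guided by ACR recommendations (8.2). This probably narrows any gap. With a cut at the mean of baseline, the unadjusted rejection rates on change at n = 500 in illustration A drop to about 5%, 6.5% and 10%.
- **A named classification standard is a defensible choice.** This stands.

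A reader might infer that the seronegative group is selected for more active disease. The documents do not support that as a fact: it needs item weights, a threshold, and a link from the entry features to activity when etanercept was started. A reader might also infer that clinician diagnosis should be the primary population. Section 6 ties RF to diagnosis as well, so that choice would not clearly take serology out of selection.

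**Conclusion.** The contradiction between 8.2 and 8.2.1 is plain from the text and must be resolved. Bias from serology in the entry rule is a reasonable possibility, not a finding. Its existence and size depend on inputs that the documents do not give. It could be nil: if nearly all diagnosed seronegative patients meet the criteria, or if the entry features are unrelated to baseline activity, nothing follows. The 34% and 68% rejection rates describe only the unadjusted test on change, with half of the diagnosed seronegative patients removed, r = 0.5, and no further selection for active disease. They are not estimates for this study.

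What does follow is that 8.6 leaves the serostatus comparison open to a baseline gap that can be inspected and adjusted for with data the protocol already collects. The near-complete correction by adjustment assumes that entry selection affects the last-visit score only through baseline activity.

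**What to change.** 1. State one population rule, in the same words, in 8.2 and 8.2.1. Either rule can serve; the text should say which one was applied.
2. Report baseline DAS28 and CDAI by serostatus.
3. In the models for last-visit DAS28 and CDAI, force in the baseline value of the same score, and keep the serostatus term so that the comparison is always reported. Base the serostatus conclusion on this adjusted comparison. Present the unadjusted tests and change scores as descriptive.
4. Where the registry records criteria status, repeat the analysis under the other population definition as a sensitivity analysis. Where it does not, say in 8.8 that serology may have been part of selection.

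The cost is small: wording in 8.2, 8.2.1, 8.6 and, if needed, 8.8, one baseline table, and one refit for each of the two outcomes. Items 1 to 3 need no new variables. Item 4 may need a further registry extract, because 8.3 does not list criteria status and a cohort built under the narrower rule would lack the other patients. Section 5 dates the final study report 29 June 2021, so in practice this is a correction to the text and a re-analysis of the existing file.

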8.4. Study Size

There is no pre-identified study size sample. All patients that meet the criteria will be entered into the study.

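### The hypothesis is no difference by serostatus, but the plan offers only difference tests at p<0.05 and no interval, so a non-significant result could not support it

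*Combined protocol and SAP*

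**What the plan says.** Under the Hypothesis heading in Section 8.2 the plan writes "Our hypothesis is that there is no difference in response between seropositive and seronegative RA patients to Enbrel". It is the only hypothesis in the document, and no alternative is stated.

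Section 8.6 forms the two groups by anti-CCP status. For continuous outcomes, "the Student's t-test will be used for normally distributed variables and the Kruskall-Wallis test for non-parametric data"; chi-squared tests cover categorical data. The adjusted analysis is a "multivariate analysis by using a stepwise linear regression model", in which RF and anti-CCP are two of the baseline variables considered. The only criterion for judging results is this: "A p-value of <0.05 is considered statistically significant, without multiplicity adjustment, for this post-hoc analysis".

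On size, Section 8.4 says "There is no pre-identified study size sample" and takes every eligible registry patient.

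The methods sections contain no confidence interval for the group difference, no clinically important difference or margin, no statement of power or precision, and no rule for reading a non-significant result. The one limitation listed in Section 8.8 is missing data.

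**The concern.** A test for a difference can count against a hypothesis of no difference, but failing to reject does not establish it. The fewer or noisier the data, the more often p≥0.05 occurs, so the hypothesis looks safest when the data say least. With no precision target, nothing in the design makes a null result informative.

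The stepwise model adds to this. If anti-CCP is not selected, the final model has no serostatus coefficient and no interval. A reader then cannot see which differences remain plausible, in exactly the case where the hypothesis would seem to have survived.

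At stake is the main conclusion. A report could state that serostatus makes no difference to etanercept response when the data are also compatible with a difference that matters.

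**Working it through.** The plan states no sample size, power, SD or margin, so it has no figure of its own to reproduce. The point is one of logic; the arithmetic only shows how large the risk could be.

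**Inputs from the documents**
- Significance level 0.05 (Section 8.6). Sidedness is not stated; two-sided is assumed.
- Share anti-CCP positive, p: 0.65 to 0.80, the background range in Section 6.

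**Assumptions, not in the documents**
- DAS28 outcome SD: 1.2 to 1.5.
- True difference, d: 0.6 DAS28 units.
- Total n: 50 to 400.

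**Formulas** (unadjusted comparison of two means, normal approximation)
- SE = SD × √(1/(n·p) + 1/(n·(1−p)))
- 95% CI half-width = 1.96 × SE
- Chance of p≥0.05 = 1 − [Φ(d/SE − 1.96) + Φ(−d/SE − 1.96)]. The last term is negligible here.

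**Two worked cases at n=100**
- Most favourable (SD 1.2, 65:35): SE = 1.2 × √(1/65 + 1/35) = 0.252. Half-width 0.49. d/SE = 2.385, and 1 − Φ(0.425) = 0.335, about 34%.
- Least favourable (SD 1.5, 80:20): SE = 1.5 × √(1/80 + 1/20) = 0.375. Half-width 0.73. d/SE = 1.6, and 1 − Φ(−0.36) = 0.641, about 64%.

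**Range over both SDs and both splits**

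| Total n | Chance of p≥0.05 if the true difference is 0.6 | 95% CI half-width |
|---|---|---|
| 50 | 61% to 80% | 0.70 to 1.04 |
| 100 | 34% to 64% | 0.49 to 0.73 |
| 200 | 8% to 38% | 0.35 to 0.52 |
| 400 | 0.2% to 11% | 0.25 to 0.37 |

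**What a null result would leave open.** Take the most favourable case at n=100 and an observed difference of 0.3. The interval is 0.3 ± 0.49, or −0.19 to 0.79. The test is non-significant, yet the interval includes both zero and 0.6. The p-value alone hides this.

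**What an equivalence claim would need.** Suppose the margin were 0.6 (assumed), the true difference zero, and an 80% chance wanted that the whole 95% CI lies inside the margin. With k = p/(1−p), the number of seronegative patients is (1.960 + 1.282)² × SD² × (1 + 1/k) / 0.6².
- SD 1.2, 65:35: 65 seronegative patients, 65/0.35 = about 186 in total.
- SD 1.5, 80:20: 83 seronegative patients, 83 × 5 = 415 in total.

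**The case against.** The strongest reply is that this is not an equivalence study. Section 7 sets out to evaluate the impact of the two markers, and the primary objective in Section 8.1 is to determine their clinical impact. The title page says an impact has already been found by others, and Section 6 looks for a predictor of response. Beside these, the sentence in Section 8.2 can be read as a conventional null hypothesis put loosely, for which a difference test is normal. This stands as a possible reading, and it removes any case for requiring an equivalence margin. It does not remove the gap, because under either reading the plan lacks an interval and guidance on a non-significant result.

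A reader might go further and infer that the plan will treat p≥0.05 as confirmation. The documents do not support that. Section 8.6 says only what counts as significant, and it calls the work post hoc. The defect is silence, which leaves that misreading open.

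The size is also uncertain. The SD, the 0.6 difference and every n are assumed. With 400 patients the risk is small under these assumptions. The calculation is unadjusted, so a model that includes the baseline score could have a smaller residual SD and a lower risk.

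Finally, the milestones in Section 5 show the final report dated 29 June 2021, and this protocol version is dated 27 July 2021. Any margin introduced now would be post hoc, even if taken from outside sources.

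**Conclusion.** The point holds as one of interpretation and reporting. The plan states a hypothesis of no difference, and its analysis can count against that hypothesis but cannot lend it support. Stepwise selection may also remove the one adjusted estimate that would show how much difference is still plausible.

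How much this matters depends on the achieved number of patients. Under the assumptions above, the chance of missing a DAS28 difference of 0.6 runs from 34% to 64% at 100 patients down to 0.2% to 11% at 400. The missing interval and the missing rule for a null result do not depend on those assumptions. The documents do not establish that the study intends to prove equivalence, or that it would report a non-significant result as proof.

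**What to change.** In Sections 8.2 and 8.6:

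1. Say whether the sentence in Section 8.2 is the null hypothesis to be tested or the claim to be shown.
2. Force anti-CCP status, which defines the groups in Section 8.6, and the baseline value of the score into the DAS28 and CDAI models, instead of leaving them to stepwise selection. Section 8.1 names RF as well, so any conclusion about RF needs the same treatment.
3. Report the seropositive-minus-seronegative difference with its 95% CI for each score, whatever the p-value.
4. State that p≥0.05 alone will not be reported as evidence of no difference.

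An equivalence claim is optional. If one is made, each score needs a margin justified from outside these data, and the whole CI must lie within it. If the margin is set after the data were analysed, label it post hoc.

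The cost is a few sentences, forced terms that are already on the candidate list, and one interval per score. No new data are needed. The downside is that the result may have to be reported as inconclusive.
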